6.2.1.4 Dosage Adjustments, Delays, Rules for Withholding or Restarting, Permanent Discontinuation

Treatment Interruption

Significant events requiring a change in treatment will be managed by immediate treatment interruption.

Note: The definition of treatment interruption may include interruption of infusion or delay of the subsequent infusion.

Events leading to treatment interruption may include:

- The subject experiences a clinically relevant grade 4 adverse event related or not-related to IP
- The subject experiences a grade ≥ 3 CRS
- Technical problem with the infusion pump / syringe pump
- The investigational product is incorrectly prepared or administered (eg, overdose)

Treatment Interruption and Re-Start in Case of Logistical Issues

If the infusion interruption or the delay of the next infusion was up to 3 days, the next dose can be administered as planned. If the infusion interruption or the delay of the next infusion was > 3 days, the instructions for re-start after interruptions due to adverse events described below should be followed.

Treatment Interruption and Re-Start in Case of Adverse Events

Specific instructions apply in case of CRS: In case of grade 2 or 3 CRS, treatment must be interrupted and delayed until the event resolves to CRS grade ≤ 1 . The Amgen medical monitor has to be consulted prior to a planned re-start. In case of grade 4 CRS, treatment must be permanently discontinued. See [section 6.6](#) for further details.

For all other adverse events, the following instructions apply:

Any clinically relevant (as determined by the investigator) grade 4 adverse event related to IP should lead to an interruption of treatment. Treatment should be interrupted until the event has resolved to grade ≤ 1 . Treatment may be resumed at the same dose or a lower dose after the event is resolved to grade ≤ 1 (see below for guidelines). Drug interruptions are also allowed in case of SAE not related to IP per investigator's discretion.

Approved

Re-start at a lower dose level:

In the following cases, the next infusion administered should be at the previous (lower) dose level:

- If the event occurred during the infusion and caused an interruption of the infusion of >72 hours, or
- if the event is defined as DLT and the subject has derived clinical benefit in the opinion of the PI after consultation with the Sponsor

In both cases, re-escalation to the target dose can be considered for the next infusion if treatment at the lower dose has been well tolerated. An intermediate dose level may be administered prior to stepping up to the target dose after consultation with the Amgen medical monitor. After the dose step, assessments of vital signs, pulse oximetry and clinical evaluation should be performed as per the schedule of assessments for D1, D2 and D3 (Table 6 for Schedule A or Table 12 for Schedule B).

Re-start at the same dose can be performed if the infusion was interrupted for < 72 hours or if the event occurred after the end of the infusion and did not cause a delay of the start of the next infusion \geq 72 hours.

In case of re-appearance of the same grade 4 adverse event, IP should be permanently discontinued.

For persistent or re-occurring clinically relevant grade 3 adverse event related to IP, a dose reduction should be considered.

In any case, restarting treatment after an interruption due to an adverse event should be performed under medical supervision. The following assessments should be performed as described in the Schedule of Assessments (Table 6 for Schedule A or Table 12 for Schedule B) for D1, D2, and D3: vital signs, pulse oximetry, and clinical evaluation. The subject should be hospitalized for at least 72 hours after re-start of the infusion.

If possible, the number of infusions at the target dose in a cycle should sum up to the planned number of infusions (ie, 2 or 4 for Schedule A or a minimum of 70% of the planned target doses for Schedule B). In this case, the subject would still be DLT-evaluable. However, if the next infusion could only be administered with a delay of 5 days, a new cycle should be started and the interrupted cycle would not be evaluable for DLT.

Permanent Discontinuation

A subject will permanently discontinue treatment with investigational product in the event of:

- Dose-limiting or other unmanageable toxicity. Exception: If a DLT occurs in a subject with a clear clinical benefit from treatment a restart at the same dose level, a lower dose and / or implementation of a dose step can be considered if the toxicity has resolved and after consultation with the sponsor
 - Grade 4 CRS.
 - Grade 2 or 3 CRS meeting any of the criteria listed below:
 - Grade 2 or 3 CRS that does not improve to \leq grade 1 within 7 days.
 - Grade 3 CRS that does not improve to \leq grade 2 within 5 days.
 - Grade 3 CRS at the initial run-in dose for a cycle (ie, at the MTD1) (for cohorts with dose step only).
 - If a subject experiences 2 separate grade 3 CRS events.
- Disease progression as defined by revised IWG response criteria ([Appendix E](#)).
- Withdrawal of subject's consent to treatment.
- Subject or investigator not compliant with the study protocol.
- Occurrence or progression of a medical condition which in the opinion of the investigator should preclude further participation of the subject in the study.
- Hematological or extramedullary relapse subsequent to CR/CRh*/CRi/morphologic leukemia-free state on protocol treatment. Exception: a blast count $> 5\%$ at the pre-dose assessment (after the infusion-free interval) would not lead to permanent treatment discontinuation even if the count had been $< 5\%$ directly after the previous treatment cycle.
- A treatment interruption of more than 21 days due to an adverse event not clearly related to the underlying disease. Exception: For patients with Grade 4 neutropenia, the infusion free period may be extended up to 42 days.
- Occurrence of CNS-related adverse event considered related to AMG 673 by the investigator and meeting 1 or more of the following criteria:
 - More than 1 seizure.
 - A CNS-related adverse event CTCAE Grade 4.
 - A CNS-related adverse event leading to treatment interruption that needed more than 1 week to resolve to CTCAE Grade ≤ 1 .
- Graft versus host disease.
- Investigator's decision that a change of therapy (including immediate HSCT) is in the subject's best interest.
- Administration of relevant non-permitted concomitant medications.
- Females who become pregnant while on study
- Males with pregnant partners or whose partners become pregnant while the subject is on study.

Approved

All reasons for treatment discontinuation should be clearly and concisely documented in the eCRF. If a subject has not continued to present for study visits, the investigator should determine the reason and circumstances as completely and accurately as possible.

In any case of premature treatment discontinuation, the investigator should make every effort to perform all examinations scheduled for the End of Treatment (EOT) and EOS visits. These data should be recorded, as they comprise an essential evaluation that should be performed prior to discharging any subject from the study and to allow for the evaluation of the study endpoints.

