1	Symptoms are not life threatening and require symptomatic treatment only, eg, fever, nausea, fatigue, headache, myalgias, malaise	
 Administer symptomatic treatment (eg, paracetamol/ acetaminophen for fever, fluids for hypotension). Consider use of tocilizumab 8 mg/kg iv. Up to 3 additional doses can be given 8 hours apart, if needed. Monitor for CRS symptoms including vital signs and pulse oximetry at least Q2 hours for 12 hours or until resolution, whichever is earlier. 	N/A
2	Symptoms require and respond to moderate intervention 
 Oxygen requirement < 40%, OR Hypotension responsive to fluids or low dose of 1 vasopressor, OR Grade 2 organ toxicity or grade 3 transaminitis per CTCAE criteria 	Administer: 
 Symptomatic treatment (eg, paracetamol/ acetaminophen for fever, vasopressors for hypotension) Supplemental oxygen when oxygen saturation is < 90% on room air Intravenous fluids or low dose vasopressor for hypotension when systolic blood pressure is < 100 mmHg. Persistent tachycardia (eg > 120 bpm) may also indicate the need for intervention for hypotension. Consider use of tocilizumab 8 mg/kg IV . Dose may be repeated every 8 hours for up to 3 additional doses. Monitor for CRS symptoms including vital signs and pulse oximetry at least Q2 hours for 12 hours or until resolution to CRS grade ≤ 1, whichever is earlier. For subjects with extensive co-morbidities or poor performance status, manage per grade 3 CRS guidance below.	Institute medical management. If hypotension worsens or persists 2 hours after adequate medical management, interrupt AMG 673 until CRS is Grade ≤ 1. Refer to re-start criteria below. If symptoms progress to grade 3 criteria, see row below. Permanently discontinue AMG 673 if there is no improvement to CRS ≤ grade 1 within 7 days.

Approved

Footnotes defined on next page of the table

Table 5. Grading and Management of Cytokine Release Syndrome

CRS Grade	Description of Severity^a	Minimum Expected Intervention	Instructions for Interruption of AMG 673

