- The Amgen medical monitor must be consulted prior to re-starting treatment
- If CRS occurred during AMG 673 infusion, infusion has been interrupted for at least 72 hours
- The event has resolved to grade ≤ 1 prior to re-starting treatment

AMG 673 therapy should be restarted 1 dose level below the dose at which the event occurred. If this lower dose level is well tolerated (ie, absence of grade ≥ 3 CRS), then a dose step up to the subject's target dose level can occur. An intermediate dose may be administered after consultation with the Amgen medical monitor prior to stepping up to the target dose.

Please also refer to the general guidance for re-start of treatment after adverse events in [Section 6.2.1.4](#)

For Grade 3 and 4 CRS, please see [Section 2](#) for DLT considerations.

Tumor Lysis Syndrome

Subjects with AML and WBC $<10,000/\text{mcl}$ or $10 \text{ cells} \times 10^9/\text{L}$ are considered to be at low risk for tumor lysis syndrome. WBC $>10,000/\text{mcl}$ and $<50,000/\text{mcl}$ are considered to be at intermediate risk, and subjects with WBC $>50,000/\text{mcl}$ are considered at high risk. This protocol requires that subjects have a maximum WBC count of $15,000/\text{mcl}$ or $15 \text{ cells} \times 10^9/\text{L}$.

Additional high-risk features include baseline uric acid $>450 \text{ mcg/L}$ (7.5 mg/dl), serum creatinine $> 1.4 \text{ mg/dL}$, and lactate dehydrogenase (LDH) greater than the ULN.

Patients with intermediate risk WBC count and elevated baseline uric acid ($> 450 \text{ mcg/L}$), serum creatinine $>1.4 \text{ mg/dl}$, or LDH greater than ULN will be recommended to receive allopurinol prophylaxis. Typical dosing is 600-800 mg/day administered BID or QID and should begin 3 days before the first dose of study drug. Patients should be well hydrated and supplemented with intravenous fluid as clinically indicated.

For grade 3 and 4 tumor lysis syndrome, please see [Section 6.2.1.3](#) for DLT considerations.

Infection Prophylaxis

Subjects who may experience neutropenia for 7 days or longer are at a high risk for infectious complications. As appropriate, these subjects should be administered prophylactic antibacterial (eg, fluoroquinolones), antifungal and antiviral medications. These subjects should be monitored for early signs of breakthrough infections after the initiation of antibacterial therapy to prompt additional evaluation and possible therapy modification.

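### Grade 2 CRS: Protocol Section 6.2.1.4 makes interruption mandatory, Table 5 makes it conditional on hypotension, and it is unclear when the Section 6.6 re-start rules apply

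*Protocol*

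**What the plan says.** **Section 6.2.1.4 (CRS instruction).** "In case of grade 2 or 3 CRS, treatment must be interrupted and delayed until the event resolves to CRS grade" 1 or less. The medical monitor must be consulted before re-start, and the reader is sent to Section 6.6 for more detail.

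**Section 6.6, Table 5, grade 2 row.** Grade 2 can be met in three ways: an oxygen requirement below 40%; hypotension that responds to fluids or to one low-dose vasopressor; or "Grade 2 organ toxicity or grade 3 transaminitis per CTCAE criteria". The interruption column begins with medical management and continues: "If hypotension worsens or persists 2 hours after adequate medical management, interrupt AMG 673 until CRS is Grade" 1 or less. It then points to the re-start criteria, refers progression to the grade 3 row, and requires permanent discontinuation if there is no improvement to grade 1 or less within 7 days. The intervention column adds: "For subjects with extensive co-morbidities or poor performance status, manage per grade 3 CRS guidance below". The grade 3 row interrupts immediately.

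**Section 6.6, re-start text below Table 5.** This sets conditions for the next infusion after any grade 2 or 3 CRS: medical monitor consulted, event resolved to grade 1 or less, and at least 72 hours of interruption if the CRS arose during an infusion. It adds: "AMG 673 therapy should be restarted 1 dose level below the dose at which the event occurred".

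**Table 5, grade 1 row.** The symptomatic treatments given as examples include "fluids for hypotension".

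The SAP does not settle the matter. It refers DLT determination and CRS grading back to the protocol.

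**The concern.** An unconditional instruction and a conditional one govern the same event, and each sits where a site would look for the answer. CRS is the only identified risk in the protocol's risk table, and Section 6.6 says it can be fatal. A site following Section 6.2.1.4 holds AMG 673 for a stable grade 2 event defined by oxygen need. A site following the grade 2 row of Table 5 finds no instruction to hold.

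The difference affects patient handling first. It can also reach the dose-finding data. Schedule B subjects must receive at least 70% of planned target doses to be DLT-evaluable (Sections 3.4 and 6.2.1.3), and the final MTD estimate uses DLT-evaluable subjects (Section 3.1). A hold, followed by a dose one level lower, uses up target doses.

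**Working it through.** **Step 1. The two interruption rules side by side.**

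| How grade 2 is met | Section 6.2.1.4 | Table 5, grade 2 row |
|---|---|---|
| Hypotension that settles with management | Interrupt | No trigger |
| Hypotension worsening, or persisting at 2 hours | Interrupt | Interrupt |
| Oxygen requirement below 40%, stable | Interrupt | No trigger |
| Organ toxicity or transaminitis, stable | Interrupt | No trigger |

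The texts agree in one row of four. Table 5's other routes (frail subjects managed as grade 3, progression to grade 3, no improvement within 7 days) do not cover a stable, resolving event in a subject who is not frail.

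**Step 2. The re-start text.** Taken alone, it covers every grade 2 or 3 CRS, so the next infusion would wait for grade 1 or less and be given one level lower even if nothing was interrupted. Table 5, however, refers to those criteria directly after its interruption instruction, which suggests that they apply only after an interruption. Neither place says which is meant.

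**Step 3. Evaluability in Schedule B.** Inputs: the 70% minimum (Sections 3.4 and 6.2.1.3) and the target-dose counts from Table 3. Formula: minimum = 0.70 × planned target doses, rounded up.

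The protocol's own examples reproduce: 0.70 × 14 = 9.8, so 10 (cohort 1); 0.70 × 12 = 8.4, so 9 (cohort 2).

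Assumed case: grade 2 CRS without hypotension at the target dose, resolved within 7 days; one daily dose held, the next given one level lower, then target again; no make-up dose. Two target doses are lost.

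| Cohort | Planned | Minimum | Can be lost | After losing 2 | Evaluable? |
|---|---|---|---|---|---|
| 1 | 14 | 10 | 4 | 12/14 (86%) | Yes |
| 2 | 12 | 9 | 3 | 10/12 (83%) | Yes |
| 3 | 10 | 7 | 3 | 8/10 (80%) | Yes |
| 4 | 8 | 6 | 2 | 6/8 (75%) | Yes |
| 5 | 6 | 5 | 1 | 4/6 (67%) | No |
| 6 | 4 | 3 | 1 | 2/4 (50%) | No |

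If nothing is held or lowered, every cohort keeps 100% of its target doses. If the event resolves before the next daily dose, only the lowered dose is lost, and cohorts 5 and 6 stay evaluable at 5/6 (83%) and 3/4 (75%). Longer holds reach further: evaluability is lost at 5 lost doses in cohort 1, 4 in cohorts 2 and 3, 3 in cohort 4, and 2 in cohorts 5 and 6.

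**Step 4. Schedule A.** Section 6.2.1.4 makes the cycle non-evaluable if the next infusion is delayed by 5 days. A shorter hold does not do so if all planned infusions are given.

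**Step 5. DLT status.** Grade 2 CRS is a DLT if it has not resolved to grade 1 or less within 7 days (Section 6.2.1.3). Both interruption rules leave that test unchanged. The event in Step 3 is therefore not a DLT, and the Section 3.4 exception for doses missed because of a DLT does not keep the subject evaluable.

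**The case against.** The strongest reply is that Section 6.6 should be read as a whole. Its re-start text speaks of all grade 2 or 3 CRS, so a site working from Table 5 and reading on would also delay the next infusion and consult the medical monitor. The disagreement would then shrink mainly to the running infusion, which lasts about 30 minutes to 3 hours. This is a fair reading, but not a settled one, because Table 5 attaches those criteria to an interruption. If it is adopted, the conflict moves to Table 5 against the text beneath it.

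Several stronger inferences are tempting and are not supported:

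- *A third threshold.* The event list in Section 6.2.1.4 includes "The subject experiences a grade ≥ 3 CRS", but the list is introduced as examples and sets no lower limit. Two rules conflict, not three.
- *Table 5 never interrupts for grade 2 CRS without hypotension.* It does so for subjects managed as grade 3 and on progression to grade 3, and it discontinues if there is no improvement within 7 days.
- *Evaluability is lost generally.* It depends on cohort, hold and make-up doses. Section 6.2.1.4 asks that target infusions still reach the required number if possible, in which case the subject remains evaluable.
- *CRS toxicity is hidden from the DLT count.* The subject dropped in the worked case has no DLT, so dropping that subject raises the observed DLT proportion. Safety data from non-evaluable subjects still go to the dose level review, and replacement is optional.
- *The grade 1 example of fluids shifts DLT classification.* Grade is set by the severity column. The example sits in the intervention column and is untidy, but the documents do not show that it changes a grade.

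**Conclusion.** The contradiction stands on the current text. Section 6.2.1.4 requires interruption for every grade 2 CRS. The grade 2 row of Table 5 requires it if hypotension worsens or persists, and it has no trigger for stable grade 2 CRS met by oxygen need or organ toxicity, outside the three routes noted above. Whether the re-start conditions and the lower re-start dose apply to an uninterrupted grade 2 event is not stated.

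The certain consequence is that sites can dose the same event differently. The effect on DLT-evaluability is conditional. With two target doses lost and no make-up it is confined to Schedule B cohorts 5 and 6. It disappears with a shorter hold or a make-up dose, and it extends to lower cohorts only with longer holds. The direction of any bias in the MTD estimate is not established. The reason to act is conflicting instructions on the main toxicity of a first-in-human trial, more than the size of the evaluability effect.

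**What to change.** Reconcile the CRS instruction in Section 6.2.1.4, the grade 2 row of Table 5 and the re-start text in Section 6.6, so that:

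- one stated condition decides interruption for each way of meeting grade 2 (hypotension, oxygen requirement, organ toxicity or transaminitis);
- the protocol says whether the re-start conditions and the re-start one dose level lower apply to a grade 2 CRS that was not interrupted.

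As a minor point, reconcile the fluids example in the grade 1 row with the grade 2 hypotension criterion. Which rule should prevail is for the sponsor to decide, and none is proposed here.

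The cost is protocol wording in Sections 6.2.1.4 and 6.6 (including Table 5) and a letter to sites. The sample size, the dose-toxicity model and the SAP need no change.

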6.3 Other Protocol-required Therapies

All other protocol-required and recommended therapies including corticosteroids, that are commercially available are not provided or reimbursed by Amgen (except if required by local regulation). The investigator will be responsible for obtaining supplies of these therapies.

Oxygen: Oxygen administration as a supportive measure is permitted during study treatment.

Hydroxyurea: Hydroxyurea for 7 days at a dose of 1 – 10 g / day is permitted prior to the first cycle of IP treatment for subjects with high WBC (> 15,000 cells/mcL or 15 cells x 10⁹/L). Administration of hydroxyurea after the start of IP must be approved and discussed with the Amgen medical monitor.

Dexamethasone: Premedication with dexamethasone is required prior to day 1 and day 5 of AMG 673 dosing and prior to each step-up dose of AMG 673 to mitigate the risk of CRS in Schedule A. For Schedule B, premedication with dexamethasone is required prior to a dose administered on day 1 and each step-up dose in cycle 1, and prior to every dose in subsequent cycles. When dosed, dexamethasone should be administered as a single IV dose (8 mg) within 1 hour of start of infusion.

Tocilizumab: Tocilizumab may be added to CRS treatment regimen or required to be used in combination with dexamethasone to treat CRS as per protocol [Section 6.6](#).

For administration of tocilizumab or dexamethasone and tocilizumab after occurrence of CRS, follow guidance in [Section 6.6](#). Additional details regarding these protocol-required therapies are provided in the IPIM.

6.4 Hepatotoxicity Stopping and Rechallenge Rules

Subjects with abnormal hepatic laboratory values (ie, ALP, AST, ALT, total bilirubin [TBL], and/or international normalized ratio [INR]) and/or signs/symptoms of hepatitis (as described below) may meet the criteria for withholding or permanent discontinuation of Amgen investigational product or other protocol-required therapies as specified in the FDA Guidance for Industry Drug-Induced Liver Injury: Premarketing Clinical Evaluation, July 2009.

6.4.1 Criteria for Permanent Withholding of AMG 673 due to Potential Hepatotoxicity

Investigational product should be discontinued permanently and the subject should be followed according to the recommendations in [Appendix A](#) (Additional Safety Assessment Information) for possible drug-induced liver injury (DILI), if ALL of the criteria below are met:

ALT or AST \geq 3.0 ULN; TBL \geq 2.0 ULN or INR \geq 1.5, ALP \leq 2.0 ULN; and no other confounding factors including preexisting or acute liver disease ([FDA, 2009](#)).

- Important alternative causes for elevated AST/ALT and/or TBL values include, but are not limited to:
 - hepatobiliary tract disease
 - viral hepatitis (eg, hepatitis A/B/C/D/E, Epstein-Barr Virus, cytomegalovirus, herpes simplex virus, varicella, toxoplasmosis, and parvovirus)
 - right sided heart failure, hypotension, or any cause of hypoxia to the liver causing ischemia
 - exposure to hepatotoxic agents/drugs or hepatotoxins, including herbal and dietary supplements, plants, and mushrooms
 - heritable disorders causing impaired glucuronidation (eg, Gilbert's Syndrome, Crigler-Najjar syndrome) and drugs that inhibit bilirubin glucuronidation (eg, indinavir, atazanavir)
 - alpha-1 antitrypsin deficiency
 - alcoholic hepatitis
 - autoimmune hepatitis
 - Wilson's disease and hemochromatosis
 - nonalcoholic Fatty Liver Disease including steatohepatitis
 - non-hepatic causes (eg, rhabdomyolysis, hemolysis)

Approved

